b Vital signs: systolic/diastolic blood pressure, pulse rate, respiratory rate, and body temperature; body weight only at Visit 0.

c Vital signs pre-dose and at 1 h (±15 minutes) on days with IMP injection.

d Dipstick urine analysis: glucose, bilirubin, ketone, specific gravity, blood, pH, protein, urobilinogen, nitrite, and leukocytes. Microscopic urinalysis: if warranted by dipstick results, urine sediment will be microscopically examined for the presence of red blood cells, white blood cells, casts, crystals, epithelial cells, and bacteria.

e Clinical laboratory tests: (Chemistry) alkaline phosphatase, creatinine, ferritin, C-reactive protein, albumin, alanine aminotransferase, amylase, aspartate aminotransferase, gamma glutamyl transpeptidase, total bilirubin, blood urea nitrogen, glucose, lipase, sodium, potassium, calcium; (Hematology) hemoglobin, hematocrit, red blood cell count, white blood cell count and differential (neutrophils, lymphocytes, monocytes, eosinophils, basophils), platelet count. Only in women who are not WOCBP (to confirm post-menopausal status): follicle stimulating hormone at Visit 0.

f Will be tested within 24 h, either at a central laboratory or a "point of care" device at the trial site or a local laboratory of the trial site.

g Oral swab for SARS-CoV-2 testing either on Day -1 or at Visit 1 on Day 1.

h Swabs will only be analyzed (sequenced) if serum nucleocapsid protein ELISA testing and/or NAAT-based SARS-CoV-2 testing detects SARS-CoV-2 (with or without symptoms). Oral swabs for SARS-CoV-2 sequencing must be collected at the same day/time (±30 minutes) as the oral swabs for NAAT-based SARS-CoV-2 for screening/surveillance.

BioNTech SE	
Confidential	

Clinical Trial Protocol BNT162-14 Page 11 of 91 Version: 4.0 Date: 20 JAN 2022

- i Only AEs related to IMP, AESIs, and SAEs. All AEs linked to confirmed COVID-19 cases will be recorded. For trial subjects who receive non-trial SARS-CoV-2 vaccinations, the AEs expected to be captured after these vaccinations are within the frame of post-marketing safety data reporting (see Section 8.3.1) and should not be recorded in the CRF.
- j Issue thermometer if not available from parent trial, for subjects to measure their body temperature each day and if they experience flu-like symptoms.

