- g Swabs will only be analyzed (sequenced) if serum nucleocapsid protein ELISA testing and/or NAAT-based SARS-CoV-2 testing detects SARS-CoV-2 (with or without symptoms). Oral swabs for SARS-CoV-2 sequencing must be collected at the same day/time (±30 minutes) as the oral swabs for NAAT-based SARS-CoV-2 for screening/surveillance.
- h Group B transplant subjects (Cohort 13 of the BNT162-01 trial) will be followed according to this SoA; BUT they will NOT receive their second vaccination on Visit 3 and no diaries will be distributed; their second vaccination will be administered based on SRC recommendation. Thereafter Group B transplant subjects (Cohort 13 of the BNT162-01 trial) will be followed according to the SoA in Table 2a.

i Issue thermometer if not available from parent trial, for subjects to measure their body temperature each day and if they experience flu-like symptoms.

PioNTook SE	Clinical Trial Drotocol	Page 14 of 91
DIDINTECTIOE		Version: 4.0
Confidential	BNT162-14	
-		Date: 20 JAN 2022

- j Only AEs related to IMP, AESIs, SAEs, and all AEs linked to confirmed COVID-19 cases will be recorded until the end of trial. For trial subjects who receive non-trial SARS-CoV-2 vaccinations, the AEs expected to be captured after these vaccinations are within the frame of post-marketing safety data reporting (see Section 8.3.1) and should not be recorded in the CRF.
- k Only for Group B transplant subjects: only AEs related to IMP, AESIs, SAEs, and all AEs linked to confirmed COVID-19 cases will be recorded until the end of trial. For trial subjects who receive non-trial SARS-CoV-2 vaccinations, the AEs expected to be captured after these vaccinations are within the frame of post-marketing safety data reporting (see Section 8.3.1) and should not be recorded in the CRF.
- I For subjects who receive non-trial SARS-CoV-2 vaccinations there will be no sampling in subsequent visits. Information about these vaccinations may be received outside of a planned visit and can be collected remotely, e.g., by phone. In such cases information on physical examination and vital signs can be skipped. However, AEs that occurred prior to administration of non-trial vaccine must be enquired and should be recorded as stated in footnotes "j" and "k".

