Blood draws for CMI (100 mL each)	Х	х	х	х	Х	Х
Issue/collect subject diaries	X (issue)	X (collect)				
Subjects report daily reactogenicity (incl. body temperature) in their diary for 7 days post each vaccination	X (post-dose)	X (post-dose)				
Record AEs since last visit	Х	Х	х	X ^f	X ^f	X ^f
Record pregnancies	=>	=>	=>	=>	End	(End)
Record concomitant medication	Х	Х	Х	X ^h	X ^h	X ^h

Clinical Trial Protocol BNT162-14 Page 16 of 91 Version: 4.0 Date: 20 JAN 2022

Note: The SoA allows for *ad hoc* SARS-CoV-2 testing for symptomatic or asymptomatic subjects.

- a Brief (symptom-directed) physical examination; no height measurement.
- b Vital signs: systolic/diastolic blood pressure, pulse rate, respiratory rate, and body temperature; body weight only at Visit 0.
- c Vital signs pre-dose on days with IMP injection.
- d (Hematology) hemoglobin, hematocrit, red blood cell count, white blood cell count and differential (neutrophils, lymphocytes, monocytes, eosinophils, basophils), platelet count.
- e Swabs will only be analyzed (sequenced) if serum nucleocapsid protein ELISA testing and/or NAAT-based SARS-CoV-2 testing detects SARS-CoV-2 (with or without symptoms). Oral swabs for SARS-CoV-2 sequencing must be collected at the same day/time (±30 minutes) as the oral swabs for NAAT-based SARS-CoV-2 for screening/surveillance.
- f Starting 28 d post injection 2, only AEs related to IMP, AESIs, SAEs, and all AEs linked to confirmed COVID-19 cases will be recorded until the end of trial. For trial subjects who receive non-trial SARS-CoV-2 vaccinations, the AEs expected to be captured after these vaccinations are within the frame of post-marketing safety data reporting (see Section 8.3.1) and should not be recorded in the CRF.
- g For subjects who receive non-trial SARS-CoV-2 vaccinations there will be no sampling in subsequent visits. Information about these vaccinations may be received outside of a planned visit and can be collected remotely, e.g., by phone. In such cases information on physical examination and vital signs can be skipped. However, AEs that occurred prior to administration of non-trial vaccine must be enquired and should be recorded as stated in footnote "f".
- h Record any non-trial SARS-CoV-2 vaccinations that trial subjects receive during the trial in the CRF until the last trial visit.

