3 OBJECTIVES AND ENDPOINTS

OBJECTIVES	ENDPOINTS	
Primary objectives	Endpoints	
To determine the safety and tolerability of one or two boosting doses of Comirnaty or one dose of BNT162b2s01 in BNT162-01 trial subjects, or two boosting doses of Comirnaty in BNT162-04 trial subjects.	 For all Group A and Group B subjects: The proportion of subjects in each treatment group with at least one SAE or the proportion of AESIs occurring up to 26 weeks after the first IMP injection. For Group A and a selected subset of Group B subjects: The frequency of solicited local reactions (pain, tenderness, erythema/redness, induration/swelling) at the injection site recorded up to 7 d after each IMP injection. The frequency of solicited systemic reactions (vomiting, diarrhea, headache, fatigue/tiredness, fever, chills, nausea, new or worsened muscle pain, new or worsening joint pain) recorded up to 7 d after each IMP injection. The proportion of subjects with at least one unsolicited TEAE occurring up to 28 d after IMP injection in each treatment group. 	
Secondary objectives	Endpoints	
To describe changes in SARS-CoV-2 neutralizing antibody titers from baseline to reference and SARS-CoV-2 variant B.1.351.	 For Group A and Group B subjects (except transplant subjects): Antibody titers to recombinant S1 and RBD protein derived from reference and SARS-CoV-2 variant B.1.351** will be assessed at baseline (Day 1) and then Day 8, Weeks 3*, 4, 7*, 12, and 26: Neutralizing antibody titers. Antibody titers (ELISA). SARS-CoV-2 functional cross-neutralization of variant B.1.351** to reference strain. *Group B only **Group B transplant subjects only: Antibody titers to recombinant S1 and RBD protein derived from SARS-CoV-2 will be assessed at baseline (Day 1) and then Day 8, Weeks 4, 12, and 26 post Dose 1, and at Dose 2 (Day 1) and then Day 8, Weeks 4, 12, and 26 post Dose 2: Neutralizing antibody titers. Antibody titers (ELISA). 	
Exploratory objectives	Endpoints	

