8.3.1 Time period and frequency for collecting AE, AESI, and SAE information

For trial subjects enrolled in this clinical trial, i.e., after transfer from the parent trial to this trial, all AEs, AESI, and SAEs (including a death) will be recorded at the time points listed in the SoA in Section 1.3. All safety reporting will occur through this rollover trial; this includes the reporting of non-vaccine related AEs that are unresolved from the parent trial.

For subjects who receive a non-trial SARS-CoV-2 vaccination, AEs/SAEs will be collected as specified above until the date when the subject was vaccinated with the non-trial SARS-CoV-2 vaccine. The AEs expected to be captured after non-trial SARS-CoV-2 vaccination are within the frame of post-marketing safety data reporting.

Investigators are not obligated to actively seek AEs or SAEs at any time after a trial subject has been discharged from the trial, however, if the investigator learns of any SAE (including a death), that they consider to be reasonably related to the IMP administration or trial participation, the investigator must promptly notify the sponsor.

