10.3.1 Definition of AE and TEAE

- An AE is any untoward medical occurrence in a trial subject, temporally associated with the use of trial treatment, whether or not considered related to the IMP.
 NOTE: An AE can therefore be any unfavorable and unintended sign (including an abnormal laboratory finding that is clinically significant), symptom, or disease (new or exacerbated) temporally associated with the use of IMP.
- Events after signing ICF and before IMP administration will be handled as AEs (also called pre-existing conditions).
- A TEAE is defined as any AE with an onset after the first IMP injection or worsened after the first IMP injection (if the AE was present before the first administration of IMP). AEs with an onset date more than 28 d after the last administration of IMP will be considered as treatment-emergent only if assessed as related to IMP by the investigator.

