6.4.3. Adverse events

Definition

For detailed information on adverse events see Section 10.3 of the protocol. Solicited AEs that are recorded from the subject diaries on the reactogenicity CRFs will not be reported as AEs unless the solicited AE meets criteria for SAE or begins after Day 8 or started before Day 8 and continues past Day 8.

Adverse events (AEs) will be coded using the Version MedDRA[®] 24.0 to get a system organ class (SOC) and preferred term (PT) for each AE.

A TEAE is defined as any AE with an onset after the first injection (Dose 1) (if the AE was absent before the first injection) or worsened after the first injection (Dose 1) (if the AE was present before the first injection (Dose 1)). AEs with an onset date more than 28 days after the last injection will be considered as treatment emergent only if

assessed as related to IMP by the investigator. AEs that cannot be determined to not be treatment emergent due to missing date or time will be defined as TEAE.

Note: To clarify the definition in the protocol, AEs with an onset date at the date of the first injection (Dose 1) will only be considered as treatment emergent if the AE occurred after the first injection (Dose 1). AEs with missing time and occurring on the day of Dose 1 or AEs with missing date will be analyzed as treatment emergent.

TEAEs will be evaluated for following time interval and groups:

- Up to 28 days after the first IMP injection (Group A and immunology subset of Group B)
- After the first IMP injection up to 28 days after the second IMP injection (immunology subset of Group B non-transplant)
- After the second IMP up to 28 days after the second IMP injection (immunology subset of Group B transplant)
- All TEAEs (Group A and immunology subset of Group B)

AEs are assigned to the time interval according to their start date and time. AEs with missing date will be assigned to each of the respective intervals if it cannot be ruled out, that it belongs to the time interval.

Adverse events of special interest (AESIs)

The following events will be reported as AESIs: myocarditis, pericarditis, anaphylaxis, thromboembolic events (e.g., deep vein thrombosis, stroke, myocardial infarction), immune thrombocytopenia and immune based neurologic events (e.g., optic neuropathy, Guillain-Barré syndrome). AESIs are recorded in the CRF.

AESIs and SAEs will be evaluated up to 26 weeks after the ICF was signed for all groups.

Analysis

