The following TEAE types will be analyzed for Group A and the immunology subset of Group B:

- Any TEAE
- Related TEAE, i.e., suspected unexpected serious adverse reactions (SUSARs) which will be described in safety reports
- Any Grade ≥3 TEAE
- Any related Grade ≥3 TEAE
- Any treatment emergent serious adverse event (TESAE)
- Related TESAE
- TEAESI

- TEAEs linked to confirmed COVID-19 cases (TEAEs with preferred term = 'COVID-19')
- Deaths

The following AE types will be analyzed for all groups if applicable:

- Any AE
- Related AE
- Any Grade ≥3 AE
- Any related Grade ≥3 AE
- Any serious adverse event (SAE)
- Related SAE
- AESI
- Related AESI
- Any AEs linked to confirmed COVID-19 cases (AEs with preferred term = 'COVID-19')
- Deaths

Overall summary of TEAEs

For Group A and the immunology subset of Group B, the number and percentage of subjects reporting at least one TEAE and the number of TEAEs will be summarized for all TEAE types defined above overall.

For Group B, the number and percentage of subjects reporting at least one

- SAE
- AESIs

will be summarized.

For Group A and the immunology subset of Group B, the number and percentage of subjects reporting at least one TEAE and the number of TEAEs will be summarized by PT nested within SOC for each of the following AE types: Any TEAE, Related TEAE, Any TESAE, Related TESAE, TEAEs leading to treatment discontinuation, solicited TEAEs and fatal TEAE.

For Group B, the number and percentage of subjects reporting at least one TESAE will be summarized by PT nested within SOC.

If a SOC and PT is reported more than once for a subject, the subject will only be counted once for this SOC and PT at the worst grade level. All TEAE summary tables will be sorted alphabetically by SOC and PT within SOC.

TEAE by grade

For Group A and the immunology subset of Group B, the number and percentage of subjects with TEAEs and TESAEs will be summarized by worst grade by PT nested within SOC by time interval.

For Group B, the number and percentage of subjects with TESAEs will be summarized by worst grade by PT nested within SOC.

The worst grade will be counted if a TEAE is reported more than once by the same subject for this SOC and PT.

AEs

The number and percentage of subjects reporting at least one AE and the number of AEs will be summarized for the above defined AE types for all groups.

SAEs

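### AE recording is restricted by visit rather than by day, so the 28-day primary TEAE proportion can lose events; separately, the SAP equates related TEAEs with SUSARs

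*Protocol*

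**What the plan says.** **Endpoint and definition.** Protocol Section 3 makes this a primary endpoint for Group A and a selected subset of Group B: "The proportion of subjects with at least one unsolicited TEAE occurring up to 28 d after IMP injection in each treatment group". SAP 6.4 applies the 28 days after each injection. Protocol 10.3.1 brings in relatedness only after that window: "AEs with an onset date more than 28 d after the last administration of IMP will be considered as treatment-emergent only if assessed as related". For non-transplant immunology subjects, SAP 6.4.3 uses the interval "After the first IMP injection up to 28 days after the second IMP injection (immunology subset of Group B non-transplant").

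**Collection.** Protocol 8.3.1 defers to the schedule: "all AEs, AESI, and SAEs (including a death) will be recorded at the time points listed in the SoA in Section 1.3". The schedule collects AEs visit by visit, each time covering the period since the previous visit.
- Table 1 (Group A), footnote i, on Visits 5, 6, 7 and Early Termination: "Only AEs related to IMP, AESIs, and SAEs. All AEs linked to confirmed COVID-19 cases will be recorded".
- Table 2 (Group B immunology), footnote j, on Visits 6 and 7: "Only AEs related to IMP, AESIs, SAEs, and all AEs linked to confirmed COVID-19 cases will be recorded until the end of trial". Footnote k applies the same limit at Visit 5, for transplant subjects only. The Early Termination cell carries no restriction.
- Table 2a (transplant subjects, injection 2), footnote f: "Starting 28 d post injection 2, only AEs related to IMP, AESIs, SAEs, and all AEs linked to confirmed COVID-19 cases". Only this footnote is tied to a day.

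**Related TEAEs.** The TEAE types in SAP 6.4.3 include "Related TEAE, i.e., suspected unexpected serious adverse reactions (SUSARs) which will be described in safety reports". Protocol 10.3.1.5 requires a SUSAR to be unexpected and serious as well as related. Protocol 9.4.2 plans related AEs as a category of their own, separate from related SAEs.

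**The concern.** The endpoint needs every unsolicited AE with onset within 28 days. The schedule stops asking for unrelated, non-serious, non-AESI, non-COVID-19 events after a particular visit, whatever day that visit took place. If it took place early, such events between the visit and day 28 need not be recorded at any later scheduled visit. The error can only go downward, it arises from visit timing alone, and no planned output shows how many subjects are affected.

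The SAP wording is a separate fault. Under the SUSAR reading, the related-TEAE row becomes a subset of the related-TESAE row in the same list. A related Grade 3 non-serious event would count as a related Grade ≥3 TEAE but not as a related TEAE. Lymphadenopathy shows what would go missing: Protocol 8.5 names it as an adverse reaction to Comirnaty, and it is not a diary item in Section 8.2.4. The proportion with any TEAE is unaffected by this second fault.

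**Working it through.** **Inputs (Protocol 1.3).**
- Group A: injection on Day 1; last unrestricted visit is Visit 4, Day 29±7, so Day 22 to 36.
- Group B immunology, non-transplant: injection 2 on Day 22±3, so Day 19 to 25; last unrestricted scheduled visit is Visit 5, Day 50±7, so Day 43 to 57.
- Transplant subjects: Visit 4 is Day 29+7, so Day 29 to 36.

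**The plan's own figures.** 29 − 1 = 28 d for Visit 4 and 50 − 22 = 28 d for Visit 5, matching the table labels. At nominal timing the loss is zero.

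**Days lost** = max(0, injection day + 28 − day of last unrestricted visit).

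*Group A.* Maximum 29 − 22 = 7 d, and 7/28 = 25%. Over the 15 permitted days the losses are 7, 6, 5, 4, 3, 2, 1 and then eight zeros, summing to 28. If the days are equally likely (assumption), the mean is 28/15 = 1.9 d (6.7% of 28), and 7/15 = 47% of subjects lose at least one day.

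*Group B immunology, non-transplant.* Maximum 25 + 28 − 43 = 10 d. The SAP interval from injection 1 is then 25 + 27 = 52 d, so 10/52 = 19%; as a share of the 28 d after injection 2 it is 10/28 = 36%. With injection 2 on Day 22 the maximum is 7 d (7/49 = 14%). Over 7 × 15 = 105 equally likely combinations (assumption), losses sum to 210: mean 2.0 d (4.0% of the interval), and 49/105 = 47% lose at least one day.

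*Transplant.* After injection 1: 29 − 29 = 0 d. After injection 2: 0 d, because footnote f is day-based.

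*Group A Early Termination on Day 28 without Visit 4.* Unrestricted recording ended at Visit 2 (Day 8 to 10), so 28 − 10 = 18 to 28 − 8 = 20 d are lost.

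**Effect on the proportion.** The documents give no expected rate. Assume a true proportion of 30% and constant hazard, so H = −ln(0.7) = 0.357. Let f be the share of the hazard coming from events the footnotes exclude, and L the interval length. Then recorded proportion = 1 − exp(−H(1 − f × loss/L)).

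| | f = 0.25 | f = 0.5 | f = 1 |
|---|---|---|---|
| Group A, average | 29.6% | 29.2% | 28.3% |
| Group A, all seen on Day 22 | 28.4% | 26.8% | 23.5% |
| Group B, average | 29.7% | 29.5% | 29.0% |
| Group B, worst case | 28.8% | 27.6% | 25.0% |

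**Does other text close the gap?** No. Section 8.3.1 refers back to the schedule. Section 10.3.1.7 asks for any AE regardless of association, but only within the period that 8.3.1 defines.

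**SUSAR wording.** A SUSAR is related, unexpected and serious; a related TEAE need only be related. SAP Appendix 1, which lists departures from the protocol's analyses, does not mention this narrowing.

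**The case against.** **On collection.** The gap vanishes at nominal timing and concerns only one class of event. Both Group A arms follow the same schedule, no hypothesis is tested, and the 23.5% figure needs every subject seen on Day 22 with the whole hazard excludable. All of that stands, and it limits the importance of the point.

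The day count can also be challenged. SAP 6.1.2 counts the injection day as day 1. On that count the maxima are 6 and 9 d, the means 1.4 and 1.5 d, and 40% of subjects are affected. The size shifts slightly; the mismatch remains. In the other direction, Section 7.1.2 allows injection 2 to be delayed, so 10 d is not a strict upper bound.

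The Early Termination case should be rare, since Section 7.2 expects few withdrawals. An amendment may also come too late: Section 10.9.3 says no parent-trial subjects were left to roll over. That affects the choice of remedy, not whether the passages conflict.

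**On the SUSAR wording.** SAP 6.4.3 has a second list with an unqualified related-AE category for all groups, and its later instruction for tables by SOC and PT says related TEAE without the explanation. Lymphadenopathy would still appear under any TEAE. A programmer might well ignore the phrase. But the second list yields only an overall count. If the stated definition is carried through, related non-serious events have no SOC/PT table by relatedness, although Protocol 9.4.2 plans one.

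**Conclusion.** Both points hold. Footnotes i and j do not support a 28-day any-TEAE endpoint when the last unrestricted visit falls early, and footnote i also fails at Early Termination. The loss is at most 7 d in Group A and 10 d in non-transplant Group B immunology subjects within the scheduled windows, with no loss for transplant subjects at scheduled visits. Under the even-spread, constant-hazard and 30% assumptions, the average understatement is at most 1.7 points (30 − 28.3) and the extreme is 6.5 (30 − 23.5). No bias between the Group A arms is shown. The documents give neither actual visit dates nor the share of excludable events, so the true size is unknown.

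The SUSAR explanation is a plain error in the SAP. It affects the related-TEAE tables only. Both points should be corrected; neither invalidates the trial.

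**What to change.** 1. **Protocol Tables 1 and 2.** Reword footnotes i and j on the model of Table 2a footnote f. All AEs with onset up to 28 d after the last injection are recorded at whichever visit they are reported, including Early Termination, and the restricted set applies only to later onset. This needs an amendment with ethics committee approval (Protocol 10.1.1). It is worth doing only while subjects are within 28 d of an injection. Sites would ask about a few more days at an existing visit.
2. **If that window has passed.** Add to SAP 6.4.3 a table, by vaccine and subgroup, of the number of subjects whose last unrestricted AE visit came before 28 d after their last injection, with the days missed. State the limitation in the report. Visit dates are already collected, so the cost is one table and one sentence.
3. **SAP 6.4.3.** Define related TEAE as any TEAE the investigator assesses as related to IMP, and delete the SUSAR explanation. This costs one phrase and no data.
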